7.2.17 Adverse Event, **Serious Adverse Event, Adverse Device Effect**
Collection/Recording/Reporting

Adverse event, **serious adverse event, and adverse device effect** information should be collected throughout the study and recorded at each study visit. Refer to Section 9 for details.

Section: 7.2.19 Laboratory Assessments, Paragraph 3

Add:

Any sample collected according to the Schedule of Assessments (Table 2-**Table 4**) may be analyzed for any of the tests outlined in the protocol and for any tests necessary to ensure subject safety.

Section: 7.2.19 Laboratory Assessments, Paragraph 4

Add:

See Table 5 for Analyte Listing (all run by central laboratory, unless otherwise noted as “Amgen/designee” or “local” laboratory. Please refer to the central laboratory manual for the complete listing of analytes run by the central laboratory):

Section: 7.2.19 Laboratory Assessments, Table 5 Header

Add:

Table 5. Analyte Listing

Section: 7.2.20 Initial Screening Phase, Bullet 13

Add:

Serious adverse event **collection/recording/reporting** (Note: Serious adverse events are to be collected after signing of the informed consent through 16 weeks after the last dose of investigational product.)

Section: 7.2.21.1 Week -4 Visit, Bullet 7

Add:

Serious adverse event **collection/recording/reporting**

Section: 7.2.22 Day 1 Visit (Prior to Randomization), Bullet 6

Add:

- **Employment status**

Section: 7.2.22 Day 1 Visit (Prior to Randomization), Bullet 8

Add:

- Serious adverse event **collection/recording/reporting**

Section: 7.2.23 Day 1 (After Randomization) and the Double-blind Treatment Phase,

Bullet 3

Add:

- **Medical and Medication History**

Section: 7.2.23 Day 1 (After Randomization) and the Double-blind Treatment Phase,

Bullet 17

Add:

- **Employment status (weeks 12 and 24/end of double-blind treatment phase)**

Section: 7.2.23 Day 1 (After Randomization) and the Double-blind Treatment Phase,

Bullet 20

Add:

- Serious and non-serious adverse event **collection/recording/reporting**. (Note: Serious adverse events are to be collected after signing of the informed consent through 16 weeks after the last dose of investigational product. Non-serious adverse events are to be collected after the first dose of investigational product through 16 weeks after the last dose of investigational product.)

Section: 7.2.24 Open-label Treatment Phase, Bullet 15

Add:

- **Employment status**

Section: 7.2.24 Open-label Treatment Phase, Bullets 17, 18, 19, and 20

Add:

- Administration of open-label AMG 334 70 mg QM SC **or 140 mg QM SC**. The first dose of open-label investigational product is to be administered only after completion of all week 24 procedures. In general, administration of investigational product should be the last procedure performed at each study visit.
- **After IRB approval of Protocol Amendment 2, the 24-week double-blind treatment phase is followed by a 76-week OLTP with dose determined by the subject's week 48 status:**
 - (1) Subjects who have already completed the week 48 visit will continue to receive AMG 334 70 mg QM SC (OL70) for a total of 76 weeks, following the open label assessments in Table 3.
 - (2) Subjects who have not yet completed the double-blind treatment phase and are not yet in the open-label phase will receive AMG 334 140 mg QM SC (OL140) upon entering the open-label phase and continue receiving open-label AMG 334 140 mg QM SC for 76 weeks.

- (3) Subjects who have not yet completed the week 48 visit but are in the open-label phase receiving AMG 334 70 mg QM SC must increase their dose to AMG 334 140 mg QM SC and continue receiving open-label AMG 334 140 mg QM SC until the week 100 visit (OL70-140) for a total open label phase duration of 76 weeks. The dose increase should be done at the first available opportunity, defined as the first visit after IRB approval of Protocol Amendment 2. Refer to Table 3 for assessments to be collected at the visit of the dose increase and 12 weeks after the dose increase. At the time of the dose increase, the End of Open Label 70 mg eCRF page will need to be completed as subjects will be transitioning from 70 mg to 140 mg.
- Serious and non-serious adverse event **collection/recording/reporting**. (Note: Serious and non-serious adverse events are to be collected through 16 weeks after the last dose of investigational product)
- **Adverse device effects collection/recording/reporting**

Section: 7.2.24 Open-label Treatment Phase, Paragraph 2

Replace:

A subject who discontinues open-label investigational product or the study during the open-label treatment phase will complete the week 76/early termination (ET) visit and the safety follow-up visit 16 weeks after the last dose of investigational product.

With:

A subject who discontinues open-label investigational product or the study during the **OLTP** will complete the week **100**/early termination (ET) visit and the safety follow-up visit 16 weeks after the last dose of investigational product.

Section: 7.2.25 Clinical Home Use Substudy (Optional)

Add:

7.2.25 Clinical Home Use Substudy (Optional)

The following procedures are to be completed during the OLTP at time points designated in the Schedule of Assessments (Table 4). At each CHU substudy visit, any assessments scheduled for the main 20120309 study visit should also be completed.

Screening:

- Obtain consent to CHU substudy
- Review of IFU for AI/pen with subject

- Register CHU consent date using the IVR/IWR System (via Additional Product Dispensing activity)
- Review for adverse events/adverse device effects/serious adverse events

Day 1:

- After confirming subject eligibility, the following procedures are to be completed:
- Register CHU randomization to randomize the subject to two 70 mg/mL AIs/pens or one 140 mg/mL AI/pen self-administration using the IVR/IWR System (via Additional Product Dispensing activity)
 - Site to instruct subject on how to self-administer AMG 334 with the AI/pen by reviewing entire IFU
 - Physical examination of subject with particular attention to any skin abnormalities in areas that might be used for IP self-administration
 - Subject self-administration using the AI/pen under site supervision
 - Review for adverse events/adverse device effects/serious adverse events
 - Product complaint recording (if applicable)
 - Study coordinator to reconcile IP (AI/pen)

Day 28:

- Study coordinator dispenses AI/pen to subject for self-administration on day 29 (IP device assigned using the IVR/IWR system via Additional Product Dispensing activity)
- Review for adverse events/adverse device effects/serious adverse events
- Product complaint recording (if applicable)
- Telephone call time scheduled for day 29 (Note, telephone visit must occur after subject has self-administered IP)

Day 29:

- Subject self-administers AMG 334 using AI/pen in non-clinic setting
- Telephone visit with study coordinator to inquire of subject if the subject administered a full, partial, or no dose of AMG 334
- If the subject was not able to administer a full dose of AMG 334, the site staff will inquire further to determine if the subject experienced a device failure or use error that prevented the full-dose administration
- Review adverse events/adverse device effects/serious adverse events
- Product complaint recording (if applicable)

Day 56:

- Subject returns IP for Study Coordinator to reconcile IP (AI/pen)
- Study coordinator dispenses AI/pen to subject for self-administration on day 57 (IP device assigned using the IVR/IWR system via Additional Product Dispensing activity)
- Review for adverse events/adverse device effects/serious adverse events
- Product complaint recording (if applicable)
- Telephone call time scheduled for day 57 (Note, telephone visit must occur after subject has self-administered IP)

Day 57:

- Subject self-administers AMG 334 using AI/pen in the non-clinical setting
- Telephone visit with study coordinator to inquire of subject if the subject administered a full, partial, or no dose of AMG 334
- If the subject was not able to administer a full dose of AMG 334, the site staff will inquire further to determine if the subject experienced a device failure or use error that prevented the full-dose administration
- Review adverse events/adverse device effects/serious adverse events
- Product complaint recording (if applicable)

Day 85: End of CHU substudy

- Subject returns IP for study coordinator to reconcile IP (AI/pen)
- Review adverse events/adverse device effects/serious adverse events
- Product complaint recording (if applicable)
- Subject continues all 20120309 study assessments and IP is administered at site as per the 20120309 protocol

Section: [7.2.26 Safety Follow-up / End of Study Visit](#), Bullet 11 and 12

Add:

- Serious and non-serious adverse event **collecting/recording/reporting**. (Note: Serious and non-serious adverse events are to be collected through 16 weeks after the last dose of investigational product)
- **Adverse device effect/recording/reporting**
- **Product complaint recording**

Section: 7.6 Sample Storage and Destruction, Paragraph 1

Add:

Any sample collected according to the Schedule of Assessments (Table 2-**Table 3**) can be analyzed for any of the tests outlined in the protocol and for any tests necessary to minimize risks to study subjects.

Section: 8.1 Subjects' Decision to Withdraw, Paragraph 1

Replace:

If this occurs, the investigator is to discuss with the subject the appropriate processes for discontinuation from investigational product and must discuss with the subject the options for continuation of the Schedule of Assessments (Table 3) and collection of data, including endpoints and adverse events. The investigator must document the change to the Schedule of Assessments (Table 3) and the level of follow up that is agreed to by the subject (eg, in person, by telephone/mail, through family/friends, in correspondence/communication with other physicians, from review of the medical records).

With:

If this occurs, the investigator is to discuss with the subject the appropriate processes for discontinuation from investigational product and must discuss with the subject the options for continuation of the Schedule of Assessments (**Table 2-Table 4**) and collection of data, including endpoints, adverse events, **adverse device effects (if applicable), and serious adverse events**. The investigator must document the change to the Schedule of Assessments (**Table 2-Table 4**) and the level of follow-up that is agreed to by the subject (eg, in person, by telephone/mail, through family/friends, in correspondence/communication with other physicians, from review of the medical records).

Section: 9.2.1 Reporting Procedures for Adverse Events and Adverse Device Effects That do not Meet Serious Criteria, Header and Paragraph 1

Replace:

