At CHU substudy day 1, areas that may be injected (upper arm, abdomen, or upper thigh) should be examined for any skin abnormalities; adverse events, serious adverse events, and adverse device effects will be collected during the CHU substudy, and will be assessed on CHU screening, day 1, day 28 (at site), and day 56 (at site) and on CHU substudy days 29 and 57 (assessed by telephone visit). Adverse event, serious adverse event, adverse device effect, concomitant medication therapies, vital signs measurement, ECGs, urinalysis, and blood draw for serum chemistry and hematology analytes, and anti-AMG 334 antibody assay will be performed as described in the main study. On the CHU substudy day 1 visit, the site should review the IFU with the subject before administration of investigational product (IP). On day 1 of the substudy, subjects will self-administer IP (two 70 mg/mL AIs/pens or one 140 mg/mL AI/pen) under clinical site supervision.

Subjects will be provided a box containing either two 70 mg/mL AI/pens or one dose of 140 mg AI/pen at the CHU substudy day 28 and day 56 visits and will self-administer IP individually without supervision at home on substudy days 29 and 57 of the CHU substudy. On CHU day 29 and day 57, site staff will call the subject at a previously scheduled time and will ask the subject which injection site was used, if the subject administered a full, partial, or no dose of AMG 334 (after explaining that a full dose means that the entire volume of the AI/pen was injected) and will document the subject's response in the electronic case report

form (eCRF). If the subject was not able to administer a full dose of AMG 334, the site staff will inquire further to determine if the subject experienced a device failure or use error that prevented the full-dose administration. Safety will be monitored as adverse events, serious adverse events, and adverse device effects.

Day 85 (clinic visit) is the end of the CHU substudy and sites will inquire about adverse events, serious adverse events, and adverse device effects. At day 85 of the CHU substudy, site staff will administer AMG 334 140 mg SC and will continue the scheduled procedures and assessments as per the 20120309 protocol. If a subject terminates the CHU substudy early, the subject may receive administration of AMG 334 140 mg SC at the site as per the 20120309 protocol and will continue 20120309 scheduled procedures and assessments as per the 20120309 protocol.

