7.2.25 Clinical Home Use Substudy (Optional)

The following procedures are to be completed during the OLTP at time points designated in the Schedule of Assessments (Table 4). At each CHU substudy visit, any assessments scheduled for the main 20120309 study visit should also be completed.

Screening:

- Obtain consent to CHU substudy
- Review of IFU for AI/pen with subject
- Register CHU consent date using the IVR/IWR System (via Additional Product Dispensing activity)
- Review for adverse events/adverse device effects/serious adverse events

Day 1:

- After confirming subject eligibility, the following procedures are to be completed:
- Register CHU randomization to randomize the subject to two 70 mg/mL AIs/pens or one 140 mg/mL AI/pen self-administration using the IVR/IWR System (via Additional Product Dispensing activity)
 - Site to instruct subject on how to self-administer AMG 334 with the AI/pen by reviewing entire IFU
 - Physical examination of subject with particular attention to any skin abnormalities in areas that might be used for IP self-administration
 - Subject self-administration using the AI/pen under site supervision
 - Review for adverse events/adverse device effects/serious adverse events
 - Product complaint recording (if applicable)
 - Study coordinator to reconcile IP (AI/pen)

Day 28:

- Study coordinator dispenses AI/pen to subject for self-administration on day 29 (IP device assigned using the IVR/IWR system via Additional Product Dispensing activity)
- Review for adverse events/adverse device effects/serious adverse events
- Product complaint recording (if applicable)
- Telephone call time scheduled for day 29 (Note, telephone visit must occur after subject has self-administered IP)

Day 29:

- Subject self-administers AMG 334 using Al/pen in non-clinic setting
- Telephone visit with study coordinator to inquire of subject if the subject administered a full, partial, or no dose of AMG 334
- If the subject was not able to administer a full dose of AMG 334, the site staff will inquire further to determine if the subject experienced a device failure or use error that prevented the full-dose administration
- Review adverse events/adverse device effects/serious adverse events
- Product complaint recording (if applicable)

Day 56:

- Subject returns IP for Study Coordinator to reconcile IP (Al/pen)

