10.1.1.4 Clinical Home Use Substudy

10.1.1.4.1 Primary Endpoint

- **Subject-reported outcome of attempted full-dose administration on day 29 and day 57**

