considered a “yes” response, and a subject report of partial or no dose administered will be considered a “no” response. The proportion of each possible pattern of responses across the 2 visits will also be estimated. Ninety-five percent confidence intervals will be provided for each group and the difference in proportions between the groups. Subject incidence of adverse events, serious adverse events, and adverse device effects will be summarized by system organ class and preferred term for subjects enrolled in the CHU substudies. Details of the analysis of the CHU substudy will be described in a separate Statistical Analysis Plan.

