Adverse event, serious adverse event, adverse device effect, concomitant medication therapies, vital signs measurement, ECGs, urinalysis, and blood draw for serum chemistry and hematology analytes, and anti-AMG 334 antibody assay will be performed as described in the main study. On the CHU substudy day 1 visit, the site should review the IFU with the subject before administration of IP. On day 1 of the substudy, subjects will self-administer IP (two 70 mg/mL AIs/pens or one 140 mg/mL AI/pen) under clinical site supervision.

Subjects will be provided a box containing either two 70 mg/mL AI/pens or one dose of 140 mg AI/pen at the CHU substudy day 28 and day 56 visits and will self-administer IP individually without supervision at home on substudy days 29 and 57 of the CHU substudy. On CHU day 29 and day 57, site staff will call the subject at a previously scheduled time and will ask the subject which injection site was used, if the subject administered a full, partial, or no dose of AMG 334 (after explaining that a full dose means that the entire volume of the AI/pen was injected) and will document the subject's response in the eCRF. If the subject was not able to administer a full dose of AMG 334, the site staff will inquire further to determine if the subject experienced a device failure or use error that prevented the full-dose administration. Safety will be monitored as adverse events, serious adverse events, and adverse device effects.

Day 85 (clinic visit) is the end of the CHU substudy and sites will inquire about adverse events, serious adverse events, and adverse device effects. At day 85 of the CHU substudy, site staff will administer AMG 334 140 mg SC and will continue the scheduled procedures and assessments as per the 20120309 protocol. If a subject terminates the CHU substudy early, the subject may receive administration of AMG 334 140 mg SC at the site as per the 20120309 protocol and will continue 20120309 scheduled procedures and assessments as per the 20120309 protocol.

Section: [3.4 Number of Subjects](#), Paragraph 4

Add:

Approximately 50 subjects may participate in the CHU substudy.

Section: 3.6.1 Study Duration for Subjects, Paragraph 1

Replace:

The planned length of participation in the study for an individual subject is up to 95 weeks, which includes the following:

With:

The planned length of participation in the study for an individual subject is up to **119** weeks, which includes the following:

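### The home-use call is conditioned on self-administration, so a subject still on IP who has not injected has no compliant call and no stated coding; the full-dose proportion can be overstated

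*Protocol*

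**What the plan says.** The CHU primary endpoint (Protocol Section 10.1.1.4.1) is "Subject-reported outcome of attempted full-dose administration on day 29 and day 57". It is collected by telephone.

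- **Timing, Section 7.2.25.** The Day 28 entry reads "Telephone call time scheduled for day 29 (Note, telephone visit must occur after subject has self-administered IP". The Day 56 entry attaches the same note to the day 57 call. Both are in the current protocol text as well as in the amendment's description of changes.
- **Timing, Section 3.2.** On both days "site staff will call the subject at a previously scheduled time and will ask the subject which injection site was used". Nothing there makes the call depend on the injection.
- **Content, Section 7.2.25.** The Day 29 and Day 57 entries describe a "Telephone visit with study coordinator to inquire of subject if the subject administered a full, partial, or no dose of AMG 334". If the dose was not full, "site staff will inquire further to determine if the subject experienced a device failure or use error that prevented the full-dose administration".
- **Coding, Section 10.5.1.** For subjects who have not discontinued IP, a report of a full dose is a yes, and "a subject report of partial or no dose administered will be considered a" no.

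Section 10.5.1 leaves further analysis detail to a separate CHU SAP, which is not among the documents. The SAP supplied describes Protocol 1.0 of June 2015 and does not cover the substudy.

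**The concern.** The visit that measures the endpoint depends, on its wording, on an event whose absence is one of the endpoint's failure answers. Take a subject who is still on IP and has not injected when the call falls due. A call made then breaches the note. A call put off until the injection is done may itself prompt the injection. If no call is held there is no subject report, and the coding rule in Section 10.5.1 works only on a report.

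The planning split in Section 10.2 does not cover this subject either. Its three categories are not attempting because IP was discontinued, responding full dose, and responding not full dose.

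The substudy asks whether people can give themselves a full dose at home, so failure to inject bears directly on its objective. If non-injectors leave the endpoint or are prompted into it, the reported full-dose proportion rises.

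**Working it through.** **Inputs (Protocol Section 10.2).** 25 subjects per arm; 5% discontinue IP; 90% of the rest report a full dose.

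**The plan's own figures.**
- Full dose: 0.95 × 0.90 = 0.855. Not full dose: 0.95 × 0.10 = 0.095.
- Half-width = 1.96 × √(p(1 − p)/25). This gives 8.54% for p = 0.05, 13.80% for p = 0.855 and 11.49% for p = 0.095. The plan states 8.5%, 13.8% and 11.5%.
- Difference between arms: 1.96 × √(2 × 0.855 × 0.145/25) = 19.52%. The plan states 19.5%.

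All four reproduce.

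**Subjects at issue.** 0.095 × 25 = 2.4 per arm. One subject is 1/25 = 4 points of an arm.

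**Effect of the note.** Let s be the share of the not-full group that has simply not injected by the scheduled call. The documents give no value, so s is varied from 0 to 1. The full-dose proportion among subjects not discontinued is then:

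- no call held and subject dropped from the denominator: 0.855 / (0.95 − 0.095s);
- call postponed and every such subject then gives a full dose: (0.855 + 0.095s) / 0.95;
- call made anyway, or a missing response kept as a no: 0.855 / 0.95.

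| s | Dropped | Postponed, full dose follows | Called anyway or kept as no |
|---|---|---|---|
| 0 | 90.0% | 90.0% | 90.0% |
| 0.25 | 92.3% | 92.5% | 90.0% |
| 0.50 | 94.7% | 95.0% | 90.0% |
| 1 | 100% | 100% | 90.0% |

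With all enrolled subjects in an arm as the base, dropping gives 0.855 / (1 − 0.095s): 85.5%, 87.6%, 89.8% and 94.5%, at most 9.0 points. If that maximum fell in one arm only, it would move the between-arm difference by 9.0 points, against the planned half-width of 19.5.

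**The case against.** A reader might infer that no dose cannot be recorded at all and that full-dose success is therefore overstated. The documents support neither statement. The call that carries the note is required to offer a no-dose answer and to explore device failure or use error. A subject who uses the pen and delivers nothing satisfies the note and is recorded as a failure.

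The note also has an innocent reading. It sits in the entries on booking the call and was probably meant to keep the call from preceding the attempt. Asking which injection site was used presupposes an attempt, and the endpoint itself refers to an attempted administration. No passage tells sites to rebook or to withhold the call.

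On the analysis side, Section 10.1.2 puts every enrolled subject in the CHU analysis set, the planning split keeps even discontinued subjects in the 25, and the separate CHU SAP may deal with missing calls. Pens are returned and reconciled at days 56 and 85, so an unused pen should come to light.

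Much of this stands, and it removes any claim of demonstrated bias. It does not remove the conflict in the wording. Attempted does not settle the matter, because Section 10.5.1 takes everyone not discontinued and counts no dose as failure. Reconciliation comes about four weeks after each home dose and does not feed a subject-reported endpoint. The visible text gives no coding for a subject still on IP who is never called.

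A reader might also infer that the two-pen arm would be affected more. The documents give no basis for that.

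**Conclusion.** The timing note in Section 7.2.25 conflicts with Section 3.2 and with the no-dose answer that the same call must be able to return. Followed literally, it conditions ascertainment on the outcome for subjects still on IP who have not injected, and the protocol does not say how they are coded.

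The full-dose proportion can be overstated but is not shown to be. Among subjects not discontinued, the inflation runs from 0 to 10 points (90% to between 90% and 100%). It rests on the planning rates, on the unknown share s, and on whether these subjects leave the denominator or are prompted to inject. The upper end needs every planned not-full answer to be a non-injection, with no partial doses and no failed attempts. The inflation is zero if sites call regardless, or if missing responses are kept as failures.

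The substudy is descriptive, with about 50 subjects and no hypothesis test. Main-study efficacy is unaffected. The change is still worth making, because it protects the substudy's primary endpoint at almost no cost.

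**What to change.** 1. **Section 7.2.25, Day 28 and Day 56.** Replace the note with an instruction to book the call for a time after the planned injection on day 29 or day 57, and to make it at that time whether or not the subject has injected. Record no dose if no injection was given on that day. An unaided injection later on the same day should not be scored as a failure merely because it followed the call. Align Section 3.2 with this wording.
2. **CHU SAP.** State that a subject still on IP with no response stays in the denominator as a no, and add an observed-only table as sensitivity.

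The cost is wording in two protocol sections and the CHU SAP, with no additional scheduled visit. Where the injection is still outstanding at the call, the site must later confirm how the day ended. The downside is that the reported full-dose rate may be slightly lower.
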